The primary endpoint will be the 2-year risk of a composite of death from any cause, hospitalization for HF, myocardial infarction, ischemic stroke, and incident or worsening nephropathy. Incident or worsening nephropathy will be defined as a sustained decrease in estimated glomerular filtration rate (eGFR) of ≥40% from baseline, a sustained decrease in eGFR of ≤10 per minute per 1.73 m2, initiation of dialysis, or kidney transplantation. A broad composite endpoint was chosen to encompass the entire spectrum of benefit shown in outcome trials across the three therapeutic areas of T2D (major adverse cardiovascular events and incident/worsening nephropathy),(7, 8), HF (cardiovascular death, HF, and incident/worsening nephropathy)(1, 2, 4, 20), and CKD (worsening nephropathy and HF).(6, 9) SGLT2-inhibitors have been shown to reduce all-cause mortality in meta

analyses,(21, 22) and this endpoint was chosen rather than cause-specific mortality due to the lack of accuracy in registry-based ascertainment of cause of death. Potential treatment and endpoint heterogeneity will be examined in secondary endpoint and subgroup analyses.

Secondary endpoints

The 2-year risks of the following secondary endpoints will be assessed:

- Death from any cause
- Hospitalization for HF
- Incident or worsening nephropathy
- Myocardial infarction
- Ischemic stroke
- Coronary revascularization
- Hospitalization for unstable angina

Participants

We will include all patients who receive a new prescription for dapagliflozin or empagliflozin during a hospital contact in Region Hovedstaden or Region Sjælland. This includes:

- Patients with T2D
- Patients with HF
- Patients with CKD

Exclusion criteria

- Patients under the age of 18
- Patients who are incapable of giving consent
- Patients who withdraw consent

Treatment

Only empagliflozin and dapagliflozin in regular doses (10 mg) will be included in the study. Prescriptions for empagliflozin 25 mg, dapagliflozin 5 mg, or in combination tablets with other drugs will not be subject to randomization. Nor will other SGLT2-inhibitors, namely canagliflozin, be subject to randomization, as only dapagliflozin

and empagliflozin are approved for treatment of both T2D, HD, and CKD, and can thus be considered equal. Physicians will still be able to prescribe combination products or canagliflozin for T2D, as per usual practice.

Sample size and power

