The primary analyses will be performed according to the intention-to-treat principle. Follow-up will be conducted until occurrence of the primary outcome or the last date of the study period, whichever comes first. Time-to-event outcomes (including the primary endpoint) will be analyzed with Cox proportional-hazards models yielding hazard ratios with 95% confidence intervals. For outcomes with competing risks cumulative event curves will be presented.

Justification of endpoints

We chose a composite endpoint consisting of death from any cause, major adverse cardiovascular events, hospitalizations for HF, and incident or worsening nephropathy. Outcome trials have shown that SGLT2-inhibitors reduce major adverse cardiovascular events in T2D,(8) cardiovascular death or hospitalizations for HF in HF,(1) and renal events in CKD, HF, and T2D.(6, 7, 20) Furthermore, meta-analyses of randomized trials have found a reduction in death from any cause associated with SGLT2-inhibitors versus placebo.(21, 22) Thus, we chose the broadest possible primary endpoint encompassing the entire spectrum of potential clinical benefit from treatment with SGLT2-inhibitors reflecting real-world clinical practice in the diverse study population. Secondary endpoints will be used to assess the individual components of the primary endpoint.

Adverse events and safety

In light of the extensive safety data on dapagliflozin and empagliflozin from previous trials,(1-9) only serious adverse events and side effects of SGLT2-inhibitors will be registered, specifically:

- Hospitalization for ketoacidosis
- Limb amputation
- Hospitalization for genitourinary infection

Hospitalization for fracture

Ethics and trial justification

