Potential participants will be identified when they are admitted to the hospital and have indication for treatment with dapagliflozin or empagliflozin as per usual practice. The participating departments will include patients automatically through the Sundhedsplatformen (Epic) prescription module for cluster randomization. This means that only patients who would have received dapagliflozin or empagliflozin regardless will be subject to randomization. As such, no screening of health records will be performed to identify study participants. Likewise, treating physicians (not limited to the prescribing physician) have discretion to halt or change the assigned treatment, regardless of inclusion in the trial, as per usual practice. Follow-up will be conducted through automatically collected registry data, resulting in no additional study visits or collection of additional non-standard data from patients. Information about the study will be provided through a pamphlet which will be handed to the patient, who can choose to opt out by informing clinical staff at the trial site orally. If a patient chooses to opt out, the treating physician will simply click a button (specifically designed for opt-out) in the randomization module in

Sundhedsplatformen and proceed to prescribe the preferred treatment, as per usual practice. The withdrawal of consent will then be automatically registered. Enrollment only occurs when the randomization is accepted in Sundhedsplatformen. As such, patients who opt out at this point will not be enrolled in the study and none of their data are collected. According to Danish and EU-legislation, informed consent can be obtained by simplified means when a cluster randomized study is conducted.

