To ensure that all participants understand the written material, this will be available in multiple languages by authorized translations. The information will be written in lay terms and will comply with what is described in the protocol and will state that the patients can refuse to participate and can withdraw at any time. If the patient is permanently incapable of understanding the written material, this patient will not participate in the study. Examples of such conditions include severe dementia or mental deficiency. The treating physicians at the trial sites will be instructed to not enroll patients in the study if they fulfill this criterion according to their own discretion. In addition, it will be pointed out that opting out will not have any influence on the patient's further treatment. One month after patients have been discharged or their outpatient contact has ended, they will also receive an email through E-boks describing that they have been included in the study and that they can choose not to participate in the study by actively withdrawing their consent. Additionally, if concerns arise regarding safety, guideline-changes, or significant price changes (threefold or more) of the investigational medicinal products, an update will be sent to study participants through E-boks.

The nurses and doctors will have received both oral and written material regarding the study, which will make them capable of answering questions regarding the study. Either the doctor or the nurse will hand out the written material to the patient (Appendix).

Consent

As of January 2022, a new regulation (EU regulation No 536/2014 of the European parliaments and of the council of 16th of April 2014 on clinical trials on pharmaceutical products for human use article 30 (informed consent in cluster trials)) has been implemented, that allows for omission of traditional informed consent in cluster randomized trials. Likewise, corresponding Danish legislation was implemented on January 1st, 2024 (LOV nr 1776 af 28/12/2023). As such, informed consent can be given based on written material, and lack of objection from the trial participants is considered as informed consent. Practically, this means that participants are given written information in accordance with the protocol, and that

the information material stipulates that the participant may refuse to participate in the study or withdraw at any point without any resulting detriment.

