Additional conditions must be fulfilled:

- a) The simplified means does not contradict national law.
- b) The methodology requires groups of participants rather than individual subjects (justified in section; Trial purpose).
- c) The clinical trial is low-intervention and that the pharmaceutical products are used in accordance with the terms of the marketing authorization (the study drugs are only investigated in patients with the indications specified in the marketing authorization, and are already used in everyday clinical practice, where the choice as of now is mainly being dictated by physician preference).
- d) There are no interventions other than the standard treatment of the subjects concerned.
- e) The protocol justifies the reasons for obtaining informed consent with simplified means and describes the information given to the patients.

Withdrawal of consent

Patients can choose to withdraw consent from the study and/or withdraw consent for usage of their data. If a patient withdraws, they will not enter the study and their data will not be used or analysed. Data regarding withdrawal will be collected via Sundhedsplatformen. The patients will be able to withdraw their consent at any time, including after the hospital contact has ended and will also receive an email via E-boks 1 month after discharge describing their participation in the study, potential significant price changes, and the possibility of withdrawing their consent. They will be instructed to notify their withdrawal of consent through secure email to [contact], which will be monitored by members of the executive committee.

Information material to patients

All patients will be given written information material when are prescribed one of the study drugs (Appendix). The information will be written in lay man terms and in different languages based on authorized translations, and will comply with what is described in the protocol and will state that the patients can refuse to participate and can withdraw at any time. In addition, it will be pointed out that opting out will not have any influence on the patient's further treatment.

Information to healthcare professionals and organization of trial sites

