- 2. The organization of training at local departments which includes physical meetings, presentations and webinars about the study. This focuses mainly on prescription of the study drugs in the randomization module in Sundhedsplatformen, as administration of either drug will not differ from current clinical practice.
- 3. The organization and monitoring of changes in Sundhedsplatformen and the software module.

Patient insurance

Insurance of patients is secured through Patienterstatningen.

Financing

The patients will have no extra costs in relation to the trial, as SGLT2-inhibitors are administered free of charge at the hospitals or purchased through a regular prescription at the pharmacy. The hospitals and patients will not have substantial additional costs, since dapagliflozin and empagliflozin currently have equal market shares in Denmark. Currently, empagliflozin costs 16 DKK/DDD for the 10 mg dosis, while dapagliflozin costs 17 DKK/DDD for the 10 mg dosis. Prices are not expected to change until expiration of the patents (2028), by when completion of follow up is planned to have occurred. In the event of price changes for two consecutive two week periods leading to a ≥1000 DKK per annum difference compared to the current price difference between empagliflozin and dapagliflozin, the executive steering committee will inform enrolled study participants about the price difference through E-boks. As only patients already being prescribed either empagliflozin or dapagliflozin will be enrolled in the study, and current choice of either drug is arbitrary, enrolment in the study will not incur extra cost to patients. The costs related to operating the trial are relatively modest and consist of consultation fees for software developers within EPIC, production of informational material, and employment of PhD fellows and postdocs. These costs are covered by an independent research grant of DKK 5,053,553 from the Novo Nordisk Foundation, Investigator Initiated Clinical Trials Grant: A Pragmatic Trial Comparing Empagliflozin and Dapagliflozin Through Cluster Randomization Embedded in the Electronic Health Record (APPLE TREE) - NNF23OC0085981.

Timeline

2023 Q3-Q4: Application for funding.

2024 Q1-Q2: Approval by authorities, information meetings at participating

departments, preparation of study initiation.

2024 Q3: First patient enrolled.

2026 Q4: Last patient enrolled (December 31).

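### The withdrawal rule removes all data whichever form of withdrawal a patient chooses, even after enrolment, which conflicts with the intention-to-treat analysis

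*Protocol*

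**What the plan says.** The Withdrawal of consent section opens with two distinct options: "Patients can choose to withdraw consent from the study and/or withdraw consent for usage of their data". The next sentence treats them alike: "If a patient withdraws, they will not enter the study and their data will not be used or analysed". The paragraph goes on to say that "The patients will be able to withdraw their consent at any time, including after the hospital contact has ended", and that an E-boks message one month after discharge will remind patients of this right.

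Four other places bear on how the rule works:

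- **Recruitment arrangements** fixes the moment of entry: "Enrollment only occurs when the randomization is accepted in Sundhedsplatformen". A patient who opts out at that point is not enrolled and contributes no data.
- **Exclusion criteria** lists "Patients who withdraw consent", with no limit on when the withdrawal occurs.
- **Statistical analyses** states: "The primary analyses will be performed according to the intention-to-treat principle". Follow-up ends at the primary outcome or at the end of the study period. Withdrawal is not named as an exception.
- **Randomization and blinding** says that patients and caretakers cannot be blinded.

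**The concern.** A two-level choice is useful only if the levels have different consequences, and here they do not. A patient who wants to leave the study but has no objection to use of registry data is removed just like one who refuses data use.

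The removal happens after randomisation, when the patient knows the drug, and it can happen after an outcome. Someone admitted for heart failure, or for a listed safety event such as ketoacidosis, who then withdraws would have that event deleted. The analysis set would no longer be everyone randomised, and membership could depend on the assigned drug and on how the patient has fared. Randomisation does not protect the comparison against that.

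The statistical analysis plan is not shown, but it could not repair this alone. It can define populations and sensitivity analyses, but it cannot analyse data that the protocol says will not be used.

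**Working it through.** **1. Can the sentence be confined to opt-out before enrolment?** The words about not entering the study suggest it. However, Recruitment arrangements already covers that case, and the Withdrawal of consent paragraph expressly includes withdrawal after the hospital contact. Those patients entered the study when the randomisation was accepted. If the sentence is confined to early opt-out, the protocol has no data rule for later withdrawal. The text needs correcting on either reading.

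**2. The plan's own figure.** Inputs from Sample size and power: 8,600 per group, 19% two-year risk, 1.9-point reduction (to 17.1%), 5% level (taken as two-sided). The normal approximation with pooled variance under the null gives power of 89.97%. The stated 90% reproduces and is not in dispute.

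**3. Loss of power.** If both arms lose the same share w, with risks unchanged, n = 8,600 × (1 − w):

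| w (assumed) | n per arm | power |
|---|---|---|
| 1% | 8,514 | 89.7% |
| 2% | 8,428 | 89.4% |
| 5% | 8,170 | 88.5% |

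Lost power is minor. Bias is the issue.

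**4. Bias with no true difference.** Let an arm with true risk 0.19 lose a share w whose risk is r. The risk among those left is

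(0.19 − w·r) / (1 − w).

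The protocol gives neither w nor r, so both are assumed. Take w = 5% in arm A and 2% in arm B.

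- r = 8%: A = (0.19 − 0.0040)/0.95 = 0.1958; B = (0.19 − 0.0016)/0.98 = 0.1922. Difference +0.0035.
- r = 30%: A = (0.19 − 0.0150)/0.95 = 0.1842; B = (0.19 − 0.0060)/0.98 = 0.1878. Difference −0.0035.

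The two mirror each other because 8% and 30% both lie 11 points from 19%.

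**5. Type I error.** With all 8,600 per arm, the standard error of the risk difference is √(2 × 0.19 × 0.81 / 8,600) = 0.00598. A shift of 0.00354 is 0.592 standard errors, so the two-sided 5% test rejects with probability P(Z > 1.960 − 0.592) + P(Z < −1.960 − 0.592) = 0.086 + 0.005 = 0.091. With the standard error from the reduced arms it is 8.9% (r = 8%) or 9.0% (r = 30%).

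**6. Range**, using the reduced arms:

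| w, A vs B | r | spurious difference (points) | type I error |
|---|---|---|---|
| 2% vs 2% | 30% | 0 | 5.0% |
| 5% vs 2% | 19% | 0 | 5.0% |
| 3% vs 1% | 30% | −0.23 | 6.7% |
| 5% vs 2% | 10% | +0.29 | 7.6% |
| 5% vs 2% | 8% | +0.35 | 8.9% |
| 5% vs 2% | 30% | −0.35 | 9.0% |
| 5% vs 2% | 38% | −0.61 | 17.5% |

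The last row is about a third of the 1.9-point target (0.61/1.9 = 0.32). Unequal withdrawal does no harm if withdrawers carry average risk (second row). Equal withdrawal can still do harm if withdrawers' risk differs between arms: at 3% in each arm, with r = 30% in A and 8% in B, the difference is 0.1866 − 0.1934 = −0.0068.

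**The case against.** The best defence is that the wording is loose and the intention sound. Recruitment arrangements uses withdrawal of consent for the opt-out button itself, so the deletion sentence and the exclusion criterion can be read as describing refusers at the point of prescription. This stands in part. It is a reason to reword the criterion instead of striking it out, but it does not supply the missing rule for later withdrawal.

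A second argument is that little remains to withdraw from except data use: there are no study visits, follow-up is by registry, and the treating physician may change the drug anyway. Consent also rests on absence of objection, so the one-month message is arguably part of the consent process. This has force. Study-only withdrawers may be few, and they can be kept only if they have been told so. Removing those who refuse data use may be unavoidable.

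A reader might also infer more than the protocol supports:

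- *That the rule removes survivors and so raises observed risk in both arms.* Withdrawers are alive only at the time they withdraw. Most follow-up may lie ahead, and a non-fatal event may already have occurred. Observed risk rises if they are at lower risk and falls if they are at higher risk.
- *That price or safety messages would empty one arm.* Recruitment arrangements and Financing address these messages to study participants, without limiting them to one arm. Reactions could differ by drug, but nothing shows that they will. Financing expects no price change before patents expire in 2028.
- *That the two price-message triggers differ by a fixed factor.* Recruitment arrangements refers to "significant price changes (threefold or more) of the investigational medicinal products"; Financing refers to a change "leading to a ≥1000 DKK per annum difference compared to the current price difference between empagliflozin and dapagliflozin". These measure different things. If empagliflozin alone tripled from 16 DKK per day, it would cost (48 − 16) × 365 = 11,680 DKK more a year, far above 1,000. If both tripled (16 to 48, 17 to 51), the gap would grow from 1 to 3 DKK per day, or 730 DKK a year, and only the first trigger would be met. The mismatch is real but is a separate, minor matter of communication.

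**Conclusion.** The point holds. As written, the Withdrawal of consent section cancels its own two-level choice and excludes randomised patients in an open-label trial, contrary to the intention-to-treat analysis that the protocol specifies. This is a defect in the stated rule, beyond a detail left for the analysis plan.

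Its numerical effect is unknown. Every withdrawal share and withdrawer risk used above is an assumption. With low withdrawal, or with balanced withdrawal at equal risk, the effect is small or nil. With moderate imbalance it is a few tenths of a percentage point, in either direction. That matters in a trial whose target is 1.9 points and whose hypothesis is no difference, since a spurious shift could create or hide one. The case for change rests on the contradiction and on how cheaply it can be removed. It does not depend on any one scenario.

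**What to change.** Separate three cases in the Withdrawal of consent section:

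1. **Opt-out before enrolment.** The patient is not enrolled and no data are collected, as Recruitment arrangements already says.
2. **Withdrawal from the study only, after enrolment.** The patient stays in the intention-to-treat analysis with registry follow-up. The information letter and the withdrawal form must say so, so that the patient's permission is clear.
3. **Explicit withdrawal of consent for data use.** The data are removed, and the number and timing of such withdrawals are reported by arm.

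Reword the exclusion criterion so that it covers only refusal before enrolment. Separately, reconcile the price-message triggers in Recruitment arrangements and Financing.

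The cost is wording in the protocol and information letter, and a withdrawal form with two options. Follow-up is already automatic, so keeping the second group needs no new visits, and the right to withdraw data is unchanged. The change should come before withdrawals are processed, because deleted records may not be recoverable.

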Appendix
